6.3 Follow-up procedures

- Treatment phase follow-up: Follow-up by phone will occur 48 hours, 1 week and 1 month after each treatment visit. A total of 24 follow-up calls will be made over the duration of the study. The purpose of the follow-up phone call is safety assessment and to document any adverse events. Calls will be made either by the clinical trial manager, the clinical research assistants, or the adverse event physician. Assessment will include the following:
 - Headache pain scale
- Long-term follow-up (Month 36, \pm 3 weeks): The purpose of the follow-up is to assess long-term safety and efficacy at the end of the study. The following exams will be conducted by the study subject's examining neurologist and study coordinator: (duration approximate 1 hour)
 - Vital signs
 - Physical exam
 - Neurological exam
 - Headache pain scale
 - EDSS
 - MSFC
 - 6 Minute Walk Test
 - 12 Item MS Walking Scale
 - MRI (brain, C and T spine) \pm Gadolinium enhancement will be scheduled to occur at end of study

6.4 Schedule of activities (Study Table)

| Tests and Assessments | Pre-treatment Phase | | | Treatment Phase, year 1 ² | | Safety FU | Outcome assessments I ³ | Treatment Phase, year 2 ² | | Safety FU | Outcome assessments II ² | Final FU ³ |
|--|--|-------------------------------|----------------------------|---|---|---|------------------------------------|---|---|--|-------------------------------------|------------------------------------|
| | Screening Visit Month -4 (Within 4 months prior to treatment phase) | Bone marrow visit Month -3 | Baseline visit Month -1 | Treatment group Months 0, 2, 4, 6, 8, 10 | Placebo group Months 0, 2, 4, 6, 8, 10 | FU by phone 48 hrs and 1 week after each treatment or placebo | All groups Month 13 | Treatment group (crossover from placebo) Months 14, 16, 18, 20, 22, 24 | Placebo group (crossover from treatment) Months 14, 16, 18, 20, 22, 24 | Follow-up by phone 48 hrs and 1 week after each treatment or placebo | All groups Month 27 | End of study follow-up Month 36 |
| ICF | X | | | | | | | | | | | |
| Serum and Plasma Biomarker Analysis Blood draw | | | | X | X | | | X | X | | | X |
| Screening Blood Draw ⁴ | X | | | | | | | | | | | |
| Bone marrow aspiration | | X | | | | | | | | | | |
| LP Procedure | | | | X | X | | | X | X | | | X |
| CSF aspiration for biomarker analysis | | | | X | X | | | X | X | | | X |
| Vital signs | X | X | X ⁵ | X | X | | X | X | X | | X | X |
| Physical exam | X | | X ⁵ | | | | X | | | | X | X |
| Neurol. exam | X | | X ⁵ | | | | X | | | | X | X |
| Headache pain scale | | X | | | X (12 total) | X | | | X (12 total) | X | X | |
| EDSS | X | | X ⁵ | X ⁶ | X ⁶ | | X | X' | X' | | X | X |
| MSFC (T25FW, 9HPT, PASAT) | | | X | X ⁶ | X ⁶ | | X | X ⁷ | X ⁷ | | X | X |
| 6 Minute Walk Test (6MW) | | | X | | | | X | | | | X | X |
| UD | | | X | | | | X | | | | X | |
| Brain, Cervical, and Thoracic MRI ±Gd | | | X | | | | X | | | | X | X |
| Twelve Item MS Walking Scale | | | X | | | | X | | | | X | X |
| Infectious disease test | X | | | | | | | | | | | |
| Pregnancy test (females) | X | | | | | | | | | | | |
| Drug & Nicotine Urine Testing | X ⁵ | | | | | | | | | | | |
| Urinalysis & Culture | | | X | | | | X | | | | X | |
| Bladder Survey | | | X | | | | X | | | | X | |
| Infectious Disease Questionnaire | X | | | | | | | | | | | |

¹Screening Blood Draw will include CBC with differential, ESR, Comprehensive Metabolic Panel, PT/PTT, and Thyroid Function Tests

²+- 1 Week Window allowed for all Treatment Phase Visits and Outcome Assessments

³+- 3 Week Window for all Final Follow-Up

Abbreviations: ICF, informed consent form; FU, follow-up; LP, lumbar puncture; UD, urodynamic testing

⁴Only required if not done during screening visit

⁵In addition to the screening period, a drug & nicotine urine testing could be done for random testing at any time during the study

⁶Only in month 6

⁷Only in month 20

7. Safety and Effectiveness Assessments:

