Stratified block randomization scheme for Phase II trial:

| EDSS | SPMS | PPMS |
|-----------------------------|-----------|-----------|
| 3.0-4.0 | 10 | 4 |
| 4.5-5.5 | 10 | 2 |
| 6.0 | 10 | 2 |
| 6.5 | 10 | 2 |
| Total # of patients: | 40 | 10 |

The total study duration will be 3 years upon enrollment. Each study subject will be required to attend up to 18 study visits, including 1 screening visit, 1 bone marrow visit, 1 baseline visit, followed by study visits every 2 months during the treatment period of two years (12 treatment/LP procedure visits and 2 outcome visits), and an additional follow-up visit at the end of year 3.

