5.6 Specimen Collection

CSF and blood specimens will be collected from all patients for exploratory biomarker discovery and validation. Approximately 10 mL of CSF will be collected at each of the 12 lumbar puncture procedures (treatment and placebo visits), just prior to intrathecal injections of the same volume of cells or saline. One additional CSF sample will be withdrawn at the month 27 follow up visit. Blood samples will also be collected at the same time as CSF collection. One approximately 6 mL blood sample will be collected in a tube with EDTA for

plasma isolation, and another approximately 6 mL blood sample will be collected in a tube without EDTA for serum isolation. All specimens will be used for research purposes to identify and/or verify biomarkers that correlate with disease progression or clinical response to IT-MSC-NP therapy. Candidate protein biomarkers, including neurofilament light, will be analyzed by single analyte ELISA or multi analyte Luminex.

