- Details regarding treatment/placebo procedures detailed in section 5.2.2 above
- Treatment visits will be conducted by the treating neurologist, [name]
- Duration of treatment visits will last approximately 5 hours
- Study subjects will be instructed to stay in bed and limit any physical activity for the 24 hours following each procedure.
- CSF for biomarker analysis discussed in 5.2.2
- Blood draw for serum and plasma biomarker analysis
- Vital Signs
- EDSS and MSFC (Month 20 Only). Follow-up by phone will occur 48 hours, 1 week, and 1 month after each treatment visit. The purpose of the follow-up phone call is safety assessment and to document any adverse events. Calls will be made either by the clinical trial manager, the clinical research assistants, or the adverse event physician. Assessment will include the following:
- Headache pain scale

Outcome assessments II (Month 27):

- The purpose of outcome assessment II visit is to evaluate effects of the treatment group in year 2 compared to the baseline visit at the beginning of year 2. In addition, these assessments will be used to evaluate any sustained effects of the treatment in year 1.
- The following exams will be conducted 3 months following the 12th treatment visit (\pm 1 week) by the study subject's examining neurologist and study coordinator
- Vital signs
- Physical exam
- Neurological exam
- Headache pain scale
- EDSS
- MSFC
- 6 Minute Walk Test
- 12 Item MS Walking Scale
- Bladder Survey
- Urinalysis and Culture to screen for UTI
- Lumbar Puncture with CSF Aspiration for biomarker analysis
- Blood draw for serum and plasma biomarker analysis
- The following exams will be scheduled to occur 3 months following the 12th treatment visit (\pm 1 week)
- MRI (brain, C and T spine) \pm Gadolinium enhancement
- Urodynamic testing of bladder compliance (ability of bladder to fill without accompanying rise in bladder pressure)

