### Exploratory Outcomes:

Individual MRI measures obtained from NeuroQuant software will be analyzed as an exploratory outcome. Brain, cervical and thoracic spine MRI scans will be obtained at baseline, and at months 13, 27, and 36. Assessments will include the following:

- Proton density and T2-weighted two-dimensional (2D) multislice turbo/fast spin-echo
- T1-weighted three-dimensional (3D) spoiled gradient recalled echo both pre-contrast and after a 10 minute delay following injection of gadolinium post-contrast sequencing
- 2D T2 weighted Fluid -Attenuated Inversion Recovery (FLAIR)
- MTR MR tractography dependent on the number of tracts followed
- DTI – A T2 SPC 3D Flair sagittal sequence, EP diffusion, and a gradient filed mapping

Using the CorTechs NeuroQuant software package a multi-structure atrophy report will be generated for all brain MRI scans as well as a Lesion Quant Flair assessment of total number and volume of lesions; the total number and volume of enlarging lesions and the total number and volume of new lesions. All lesions to be counted would have to be at least 3 voxels in size. For lesions to be considered enhancing an increase in intensity by at least 20% on the post-contrast images compared to the baseline T1 sequence lesions. The total number of new or enlarging T2 hyperintense lesions as detected by MRI will be assessed by a negative binomial model. Percentage change in total brain volume from baseline to month 13 will be assessed using an MMRM analysis.

CSF biomarker analysis will also be included as an exploratory outcome. CSF, plasma, and serum samples will be obtained at the time of each treatment, and 3 months following the 12th treatment, for a total of 13 samples of each type.

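### The schedule of activities marks the last lumbar puncture, CSF and biomarker blood sampling at Month 36, while the protocol text and SAP put this single 13th sampling at Month 27

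*Protocol*

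**What the plan says.** Four places in the text bear on the sampling that follows the twelve treatment or placebo procedures.

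- Protocol 5.6 (Specimen Collection): "One additional CSF sample will be withdrawn at the month 27 follow up visit". On blood, it adds: "Blood samples will also be collected at the same time as CSF collection".
- Protocol 6.2, Outcome assessments II (Month 27), lists "Lumbar Puncture with CSF Aspiration for biomarker analysis" and a biomarker blood draw. The visit is timed as follows: "The following exams will be conducted 3 months following the 12th treatment visit".
- SAP 4.1 (Exploratory Outcomes) places CSF, plasma and serum sampling at every treatment and once more 3 months after the 12th "treatment, for a total of 13 samples of each type".
- Protocol 6.3 describes the Month 36 visit as lasting about 1 hour. Its list of examinations has no lumbar puncture, no CSF sample and no biomarker blood draw.

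The schedule of activities in Protocol 6.4 differs. Its lumbar puncture row is "LP Procedure | | | | X | X | | | X | X | | | X", and the CSF and biomarker blood-draw rows carry marks in the same cells. Protocol 6 opens by referring the reader to this table for the timing of assessments.

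**The concern.** The schedule table is what coordinators normally work from, and here the protocol itself directs them to it. If the table and the text name different visits, the visit at which a subject has a lumbar puncture depends on which page is open. This matters more than a misplaced questionnaire would. The procedure is invasive, and Protocol 5.1 calls for an antibiotic infusion of about four hours before every lumbar puncture, which does not fit a Month 36 visit of about 1 hour.

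There is also an analytic consequence. The SAP describes the last CSF, plasma and serum samples as taken 3 months after the twelfth treatment. Samples collected according to the table would not fit that description, and a mixture of the two timings would put samples of different ages since treatment under one label.

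**Working it through.** **1. The plan's own count.** Protocol 3 gives "12 treatment/LP procedure visits and 2 outcome visits": 6 procedures in year 1 and 6 in year 2. With the one further sampling, 6 + 6 + 1 = 13, which reproduces the SAP's figure. The table also gives 12 + 1 = 13. The conflict is therefore about when the 13th sampling takes place. Its number is not in dispute.

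**2. Position of the marks.** The table has twelve visit columns: (1) screening, (2) bone marrow, (3) baseline, (4) and (5) the two year-1 groups, (6) telephone follow-up, (7) Month 13, (8) and (9) the two year-2 groups, (10) telephone follow-up, (11) Month 27, (12) Month 36. Splitting rows into cells gives:

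| Row | Marked cells | Agrees with text? |
|---|---|---|
| Biomarker blood draw | 4, 5, 8, 9, 12 | Not the last mark |
| Lumbar puncture | 4, 5, 8, 9, 12 | Not the last mark |
| CSF aspiration | 4, 5, 8, 9, 12 | Not the last mark |
| Urodynamics, urinalysis, bladder survey | 3, 7, 11 | Yes |
| 6-minute walk, MRI, 12-item walking scale | 3, 7, 11, 12 | Yes |
| Headache pain scale | 2, 5, 6, 9, 10, 11 | No, whole row |

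**3. Could the three marks be a table-reading fault?** Moving every headache mark one column to the right gives 3, 6, 7, 10, 11, 12 (baseline, telephone calls, Months 13, 27 and 36), which is what the text says. That row is displaced to the left as a whole. The three disputed rows behave differently: the first four marks are in the right place, and only the last differs from the text, by one column to the right. A uniform shift cannot produce that. The urodynamics, urinalysis and bladder survey rows show that the same copy of the table can hold a last mark at Month 27 with Month 36 empty.

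**4. Size of the timing difference.** The twelfth procedure is at Month 24, and the sixth at Month 10.

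- Since the last procedure: 27 − 24 = 3 months, against 36 − 24 = 12 months.
- Since the last cell dose, placebo-first group (cells in year 2): the same, 3 against 12 months.
- Since the last cell dose, cells-first group (cells in year 1): 27 − 10 = 17 months, against 36 − 10 = 26 months.

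Either way, the final sample moves by 9 months.

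**The case against.** The strongest reply is that the finding depends on the column position of one mark in each of three rows of a table whose supplied copy is unreliable. The headache row is displaced throughout. Some footnote marks do not match their notes: the screening blood draw carries 4 where the matching note is 1, and the baseline marks carry 5 where the matching note is 4. Rows marked at both Month 27 and Month 36, such as EDSS, MSFC and MRI, cannot show whether a single last mark has slipped. The narrative is unanimous for Month 27, and no passage of text supports a lumbar puncture at Month 36. All of this stands as a reason for caution and for checking the source table first. It does not dispose of the point, for the reasons in step 3 of the working.

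A reader might infer more than the documents support, in three ways.

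- **That subjects will have the procedure twice.** Following both sources would give 12 + 2 = 14, but Protocol 5.6 allows for a single extra CSF sample and the SAP fixes the total at 13. A second puncture would breach both, so a count of extra procedures across the trial would be speculation.
- **That Month 36 is distinctly less safe because no contact follows it.** The scheduled telephone calls are tied to treatment visits, so Month 27, an outcome visit, has no stated calls either. Protocol 8.2.2 gives all patients a 24-hour hotline.
- **That the final sample is meant to be paired with clinical response at Month 27.** Protocol 5.6 seeks biomarkers related to progression or response but names no visit.

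**Conclusion.** As supplied, Protocol 6.4 contradicts Protocol 5.6, 6.2 and 6.3 and SAP 4.1 on the visit for the 13th lumbar puncture, CSF sample and biomarker blood draw: Month 36 in the table, Month 27 in the text. The consequences are an invasive procedure that could be done at a visit the text does not name, and a final sample 12 months after the last procedure where the SAP describes 3.

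The conclusion assumes that the sponsor's source table carries these marks where the supplied copy shows them. That is unconfirmed, so confidence is low to moderate. If the source table has the marks at Month 27, the point falls away.

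The statistical reach is small. The SAP treats these biomarkers as exploratory, no listed secondary endpoint uses this sample, and the primary comparison at Month 13 comes before either visit. The point still deserves correction because it governs the timing of an invasive procedure. Which visit is right is for the sponsor to state and is not judged here.

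**What to change.** 1. Check the blood-draw, lumbar puncture and CSF rows of Protocol 6.4 in the source document.
2. If the marks are at Month 36, reconcile those rows with Protocol 5.6, 6.2 and 6.3 and SAP 4.1, so that all name the same visit and the same total number of lumbar punctures. The stated length of that visit should also be consistent with the preparation described in Protocol 5.1.
3. If any 13th samples have already been taken at the other visit, add a line to the SAP that they are analysed by actual collection date and not pooled as samples taken 3 months after the twelfth treatment.

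The cost is a look at one table, a clarification of three rows and, if needed, one sentence in the SAP. No procedure, visit or subject is added.

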7.2 Safety assessments

Research subjects will be routinely assessed for safety at all study visits and during follow-up telephone calls. Subjects will also be consistently asked to complete the headache pain scale. Safety assessments include monitoring for adverse events, vital signs, physical and neurological examination, and MRIs.

Information regarding a history of a previous positive COVID-19 test or inoculation with a COVID-19 vaccine will be collected.

7.2 Effectiveness assessments

Research subjects will be evaluated for effectiveness by EDSS, urodynamic testing, MSFC, 12 item MS walking scale, time to disability progression, progression on MRI (total T2 lesion volume and total brain volume), and 6-minute walk test.

8. Adverse Event Reporting:

8.1 Adverse event definitions

Adverse event means any untoward medical occurrence associated with the use of the drug in humans, whether or not considered drug related.

Adverse reaction means any adverse event caused by a drug.

Suspected adverse reaction means any adverse event for which there is a reasonable possibility that the drug caused the adverse event. Suspected adverse reaction implies a lesser degree of certainty about causality than “adverse reaction.”

- *Reasonable possibility.* For the purpose of IND safety reporting, “reasonable possibility” means there is evidence to suggest a causal relationship between the drug and the adverse event.

Life-threatening, suspected adverse reaction. A suspected adverse reaction is considered “life-threatening” if, in the view of either the Investigator (i.e., the study site principal investigator) or Sponsor, its occurrence places the patient or

research subject at immediate risk of death. It does not include a suspected adverse reaction that had it occurred in a more severe form, might have caused death.

Serious, suspected adverse reaction. A suspected adverse reaction is considered “serious” if, in the view of the Investigator (i.e., the study site principal investigator) or Sponsor, it results in any of the following outcomes: death, a life-threatening adverse reaction, inpatient hospitalization or prolongation of existing hospitalization, a persistent or significant incapacity or substantial disruption of the ability to conduct normal life functions, or a congenital anomaly/birth defect.

- Important drug-related medical events that may not result in death, be life-threatening, or require hospitalization may be considered “serious” when, based upon appropriate medical judgment, they may jeopardize the research subject and may require medical or surgical intervention to prevent one of the outcomes listed in this definition. Examples of such medical events include allergic bronchospasm requiring intensive treatment in the emergency room or at home, blood dyscrasias or convulsions that do not result in inpatient hospitalization, or the development of drug dependency or drug abuse.

Unexpected, suspected adverse reaction. A suspected adverse reaction is considered “unexpected” if it is not listed in the general investigational plan, clinical protocol, or elsewhere in the current IND application; or is not listed at the specificity or severity that has been previously observed and/or specified.

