3.1 Study design schematic

3.2 Allocation to treatment

A total of 50 study subjects will be enrolled according to inclusion/exclusion criteria. Subjects will be randomly assigned to placebo or treatment group according to the stratified block randomization scheme described above in section 3. A master randomization assignment list will be generated and kept in a locked secure location accessible only by PI ([name]) and co-PI ([name]), who are the only two un-blinded investigators in the study. [name] will remain un-blinded in order to coordinate autologous cell manufacturing for subjects in the treatment group. The PI will be responsible for maintaining the blind.

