8.2.2 Recording requirements

All observed or volunteered adverse events (serious or non-serious) and abnormal test findings, regardless of study group or suspected causal relationship to the study drug(s) will be recorded in the subjects’ case histories. For all adverse events, sufficient information will be pursued and/or obtained so as to permit 1) an adequate determination of the outcome of the event (i.e., whether the event should be classified as a *serious adverse event*) and; 2) an assessment of the causal relationship between the adverse event and the study drug(s).

Adverse events or abnormal test findings felt to be associated with the study drug(s) will be followed until the event (or its sequelae) or the abnormal test

finding resolves or stabilizes at a level acceptable to the safety assessing neurologist ([name] or [name]). Whichever neurologist is seeing the subject for assessments will not be the neurologist assessing safety for that subject. Each subject will have a separate examining neurologist and safety assessing neurologist. Monitoring and adjudication of all adverse events (serious or non-serious) will be performed in a sequential reporting manner. All patients will be provided a 24-hour hotline for reporting of any adverse effects. Initial screening will be performed by the clinical nursing team and all adverse events will be reported to the corresponding safety assessing neurologist for further evaluation. The treating and examining neurologists will not be involved in the notification of any adverse effects. Adjudication of all adverse events (serious or non-serious) will be determined by one of the safety assessments neurologist (sub-investigators [name] or [name]). Additionally, all serious adverse events will be reported to the DSMB immediately (24 to 48 hours) and they will adjudicate the adverse event and recommend unblinding, if necessary. Any non-serious adverse events will be reported to the DSMB on a half-yearly basis.

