8.2.2.1 Abnormal test findings

An abnormal test finding will be classified as an *adverse event* if one or more of the following criteria are met:

- The test finding is accompanied by clinical symptoms
- The test finding necessitates additional diagnostic evaluation(s) or medical/surgical intervention; including significant additional concomitant drug treatment or other therapy
 - Note: simply repeating a test finding, in the absence of any of the other listed criteria, does not constitute an adverse event.
- The test finding leads to a change in study drug dosing or discontinuation of subject participation in the clinical research study
- The test finding is considered an adverse event by the Sponsor-Investigator of the IND application

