8.2.2.2 Causality and severity assessment

One of the safety assessments neurologist (sub-Investigators [name] or [name]) of the trial will promptly review documented adverse events and abnormal test findings to determine 1) if the abnormal test finding should be classified as an adverse event; 2) if there is a reasonable possibility that the adverse event was caused by the study drug(s); and 3) if the adverse event meets the criteria for a *serious adverse event*.

If the final determination of causality is “unknown and of questionable relationship to the study drug(s)”, the adverse event will be classified as *associated with the use of the study drug(s)* for reporting purposes. If the final determination of causality is “unknown but not related to the study drug(s)”, this determination and the rationale for the determination will be documented in the respective subject’s case history.

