8.3.2 Reporting adverse events to the responsible IRB

In accordance with applicable policies of WIRB (Western Institutional Review Board), the Sponsor-Investigator will report, to the IRB, any observed or volunteered adverse event that is determined to be 1) *associated with the investigational drug or study treatment(s)*; 2) *serious*; and 3) *unexpected*. Adverse event reports will be submitted to the IRB in accordance with the respective IRB procedures.

Applicable adverse events will be reported to the IRB as soon as possible and, in no event, later than 10 calendar days following the sponsor-investigator's receipt of the respective information. Adverse events which are 1) *associated with the investigational drug or study treatment(s)*; 2) *fatal or life-threatening*; and 3) *unexpected* will be reported to the IRB within 24 hours of the Sponsor-Investigator's receipt of the respective information.

Follow-up information to a reported adverse event will be submitted to the IRB as soon as the relevant information is available. If the results of the Sponsor-Investigator's follow-up investigation show that an adverse event that was initially determined to not require reporting to the IRB does, in fact, meet the requirements for reporting; the Sponsor-Investigator will report the adverse event to the IRB as soon as possible, but in no event later than 10 calendar days, after the determination was made.

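### Section 8.1 defines serious only for suspected drug reactions, as judged by the unblinded PI or the Sponsor; other sections give seriousness to a safety neurologist, and SAP 4.2 does not say whose label it analyses

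*Protocol*

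**What the plan says.** **Seriousness.** Protocol 8.1 defines *serious* only for a suspected adverse reaction, meaning one with a reasonable possibility that the drug caused it. Such a reaction is serious if, "in the view of the Investigator (i.e., the study site principal investigator) or Sponsor, it results in any of the following outcomes". Life-threatening status is likewise decided "in the view of either the Investigator (i.e., the study site principal investigator) or Sponsor". The added clause on important medical events is also limited to drug-related ones.

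Section 8.2.2.2 has a safety-assessing neurologist, who is a sub-investigator, decide causality and whether an event meets the criteria for a serious adverse event. Section 8.2.2 gives that neurologist adjudication of all adverse events and adds that the DSMB adjudicates the serious ones, which reach it within 24-48 hours.

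**Abnormal tests.** Section 8.2.2.1 lists four alternative criteria, the last being "The test finding is considered an adverse event by the Sponsor-Investigator of the IND application". Section 8.2.2.2 asks the safety neurologist "to determine 1) if the abnormal test finding should be classified as an adverse event".

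**Blinding and routing.** The PI is the unblinded treating clinician (sections 3 and 5.1). Section 3.2 describes the PI and co-PI as those "who are the only two un-blinded investigators in the study". Section 8.2.2 routes reports through a hotline and nursing staff to the safety neurologist and says "The treating and examining neurologists will not be involved in the notification of any adverse effects".

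**Analysis.** SAP 4.2 tabulates serious events, severity and relationship, and specifies p-values for binary safety outcomes. It names no classifier and gives no definition of serious.

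**The concern.** Safety and tolerability are the trial's stated secondary objective, and the comparison of serious events between arms is part of the evidence for it. That comparison is fair only if an event receives the same label whichever arm it arose in. Section 8.2.2 goes to some trouble to secure this by keeping the treating and examining neurologists out of the route. Section 8.1 then places the word *serious* in the hands of the PI, who knows the arm, or the Sponsor, and ties it to causation by the drug.

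Two things are at stake. Arm knowledge could enter the count of serious events. And serious harm from the procedures common to both arms (the puncture and the antibiotic infusion) could go unlabelled, although these are the main harms a subject can suffer during a placebo period. An event not labelled serious also misses the 24-48 hour report to the DSMB.

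**Working it through.** No calculation applies. The question is who makes each decision, and by what test.

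**Step 1. Set the sections side by side.**

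| Decision | Protocol 8.1 or 8.2.2.1 | Protocol 8.2.2 or 8.2.2.2 |
|---|---|---|
| Serious | PI or Sponsor; suspected drug reactions only | Safety neurologist, for any adverse event; DSMB adjudicates serious ones too |
| Abnormal test is an adverse event | Any one of four criteria; the fourth is the Sponsor-Investigator's view | Safety neurologist |
| Causality | Test stated (reasonable possibility), no assessor named | Safety neurologist |

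No section says whose view prevails.

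**Step 2. Who knows the arm.** The PI does. The safety neurologists are blinded by inference: section 3.2 limits unblinding to two investigators, and these neurologists are other sub-investigators. Section 3 and SAP 1.2 name only the patient and the examining neurologist as blinded.

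**Step 3. Apply the one written definition of serious to three cases.** Section 5 identifies the drug as the cell product.

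- *Hospitalisation after a placebo puncture.* An assessor who knows that no cells were given cannot find a reasonable possibility that the drug caused it, so the event cannot qualify. A blinded assessor could still suspect the drug, so the event could qualify. After a cell injection, the same hospitalisation could qualify with either assessor. Applied with knowledge of the arm, the definition is therefore asymmetric and loses serious events from the placebo side.
- *Hospitalisation attributed to the antibiotic infusion.* Both arms receive it. The event is not a suspected reaction to the cells, so it falls outside the definition in either arm.
- *Hospitalisation judged unrelated.* It is outside the definition by construction, and the judgement of relatedness can itself depend on knowing the arm.

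**Step 4. Look for a second definition.** Section 8.2.2.2 refers to the criteria for a serious adverse event, and section 8.2.2 links that status to the event's outcome, but neither lists the qualifying outcomes. SAP 4.2 lists serious events and relationship as separate items, which suggests that causality is not meant to be a condition, but it does not say so.

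**Step 5. Follow an event to the DSMB.** The 24-48 hour rule starts once an event is called serious. Under section 8.2.2, non-serious events go to the DSMB half-yearly. DSMB adjudication can therefore check a label of serious, but it does not promptly reach an event that never received one.

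**Step 6. Reporting clocks.** The FDA limits (15 and 7 days, sections 8.3.1.1 and 8.3.1.2) run from the Sponsor-Investigator's receipt together with a determination. The IRB limits (10 days and 24 hours, section 8.3.2) run from receipt alone. The documents do not define Sponsor-Investigator and describe no hand-off from the safety neurologist.

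**The case against.** The best defence is that the sections serve two purposes. On this reading, 8.1 defines the serious suspected reaction that triggers an IND report, while 8.2.2 and 8.2.2.2 govern the serious adverse event used for recording and analysis. Section 8.2.2 requires every event to be recorded whatever the arm or suspected cause, and treats causality as a separate question. This may well be what was meant, and it shows that events are not lost from the record. It does not supply the missing definition or tell the analyst whose label to use.

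A second defence is that the PI, the Sponsor and the Sponsor-Investigator are given only the power to add: either view suffices in 8.1, and the fourth criterion in 8.2.2.1 is an alternative to three others. Nothing lets them overrule the safety neurologist downwards. That is correct, but adding events with knowledge of the arm also biases a comparison. DSMB adjudication is a real safeguard, within the limit shown in step 5.

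Several stronger readings are tempting and are not supported:

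- *That the reporting clocks contradict section 8.2.2.* This needs the Sponsor-Investigator to be the PI, which is plausible at a single site but never stated. It also needs the bar on notification to cover regulatory filing; the sentence follows the hotline and nursing steps and may concern only intake. What is certain is that the hand-off is unwritten.
- *That every abnormal test finding is affected.* Only findings that meet none of the other three criteria depend on the Sponsor-Investigator's view.
- *That marrow-aspiration events bias the arm comparison.* Section 9.4 summarises events from the first lumbar puncture onwards, and the aspiration comes about three months earlier.
- *That the effect is 4 percentage points.* One event in 25 subjects is 4 points for any binary outcome. It is not evidence that any event would be mislabelled.

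**Conclusion.** The concern holds. The protocol gives seriousness to two different roles, one of which includes the unblinded PI, and its only written definition of serious is restricted to suspected reactions to the drug. If 8.1 is followed, the serious-event comparison in SAP 4.2 can be biased by knowledge of the arm, and some serious events, including those after a placebo puncture, meet no written test and may miss the 24-48 hour DSMB report.

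The size is not estimable, since the documents give no expected rate of serious events. The direction is not fixed either: the drug-only definition removes events from placebo periods, whereas discretionary upgrading or judgements of relatedness could go either way.

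The conclusion rests on two assumptions: that the safety neurologists are blinded, which is inferred from section 3.2, and that 8.1 could be the definition applied in practice. It does not depend on who the Sponsor-Investigator is. Nothing in the documents shows that an event has been mislabelled. This is a change that should be made, and the point about the reporting clocks is a lesser clarification.

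**What to change.** 1. In protocol 8.1, define *serious adverse event* by outcome alone, regardless of causality, arm or the procedure that preceded it. Keep *serious suspected adverse reaction* as the subset used for IND reports.
2. In protocol 8.2.2 and SAP 4.2, state that the safety analysis uses the safety-assessing neurologist's classification, and state that this neurologist is blinded. Keep any upgrade by the PI, Sponsor or Sponsor-Investigator under 8.1 or 8.2.2.1 for regulatory reporting only, and record it separately.
3. As a lesser clarification, define Sponsor-Investigator, and reconcile 8.2.2 with 8.3 by stating the hand-off that starts each of the four clocks. Filing should not wait for a locked classification, because that could delay an urgent report.

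The cost is a wording amendment to the protocol and SAP and a place to record upgrades. No new staff are needed, since the safety-assessing neurologists are already in post. If events have already been classified, they would need to be re-read under the new definition by the blinded neurologist.
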